#### **Inclusion criteria**

- All Woredas in North Shewa zone will be included in the study.
- All managerial and administrative Woreda staff.

#### **Exclusion criteria**

Study participants who do not consent will be excluded.

**Timing:** the baseline study will be conducted in early August 2019, prior to the DIPH-training of Woreda staff, while the end-line survey will be conducted in late July 2021, after the end of the sixth DIPH cycle.

**Study participants:** The survey respondents will be the head of the health department, all programme officers and data managers at the district level. All eligible district staff will be interviewed, except those working in their respective districts for less than six months. We anticipate on average 6 - 7 eligible staff would be available in each Woreda and we aim to include all of them in the study.

Table 1. Sample size for before-vs.-after comparison

Indicator	Expected level at baseline	Expected Minimum percentage point increase	Health management staff assessed/ Woreda	No. of Woredas study arm
Health Information System performance at the district level	50%	25%	6	12

The sample size estimations for the required number of Woredas required per study arm is based on the statistical formula recommended by Hayes et al10. i.e.

$$c = 1 + (z_{\alpha/2} + z_{\beta})^2 \frac{\pi_0(1-\pi_0)/m + \pi_1(1-\pi_1)/m + (k_0^2\pi_0^2 + k_1^2\pi_1^2)}{(\pi_0 - \pi_1)^2}$$

Based on the calculations reported in Table above, a minimum sample size of 72 health management staff per study arm (144 in total) would have 80% power to detect a difference of at least 25 *percentage points* as statistically significant.

Where:-

C is number of clusters required (Woredas)

$Z_{\alpha/2}$  is confidence level (95%)

$Z_{\beta}$  is required power (80%)

$\pi_0$  is true proportion in the absence of intervention (50%)

$\pi_1$  is true proportion in the presence of intervention (75%)

m is individuals sampled in each cluster/woreda (72)

$k_0$  is coefficient of variation of true proportion in the absence of intervention (0.096942)

$k_1$  is coefficient of variation of true proportion in the presence of intervention (0.096942)

Based on the calculations reported in Table above, a minimum sample size of 72 health management staff per study arm (144 in total) would have 80% power to detect a difference of at least 25 *percentage points* as statistically significant.

**Data-collection:** After a detailed pilot testing (Appendix: DIPH Study Instruments, section B) , baseline survey data-collection will be carried out by DIPH field teams. For end-line survey data-collection, an independent team of four data-collectors and one supervisor will be recruited from the zone for one month. Data-collectors will be recruited by EPHI and will, as a minimum, have a Master's degree. Their classroom training on the survey instruments will be followed by a written assessment on the survey contents. Data-collectors will be provided with a field manual for reference during fieldwork. Job descriptions – with the roles and responsibilities of each team member, and expected day-to-day deliverables - will be provided. The survey will be piloted to test survey procedures and tools, and a detailed standard operating-procedures document for the survey will be provided to the data-collection team.

## Data Analysis Plan

The Primary outcomes of the study includes

- a) Change in 'Health Information System performance' at the district level over as compared to non-DIPH districts

It refers to changes in the a) Behavioural (the knowledge, skills, attitudes, values, and motivation of the people who collect and use data) and b) Technical (data collection forms, processes, systems, and methods) aspects of the district health system

*Key constructs:*

- 1) essential infrastructure for data management,
- 2) data diversity,
- 3) reporting timelines,
- 4) data-quality assessment mechanisms, and
- 5) data use.

**b) Change in Governance of data-driven decision-making at the district level level as compared to non-DIPH districts .**

It refers to changes in the **organizational** aspects of district health system (information culture, structure, resources, and roles and responsibilities of key contributors at each level of the health system. )

*Key constructs:*

- 1) evidence-based decision-making,
- 2) participatory decision-making,
- 3) understanding value of data,
- 4) health system support for data-use/data-driven decision-making, and
- 5) accountability).

The primary outcomes are the survey-based assessment indices developed by Performance of Routine Information System Management (PRISM) Toolkit (<https://www.measureevaluation.org/resources/publications/tl-18-13/index.html>). They will be created by summing the survey item's responses and converting scores to fall on a standardized scale of 0-100.

Study data will be analysed using descriptive, inferential and regression statistics. Chi-square and t-test will be used to compare sample characteristics between DIPH and non- DIPH study aims to assess the differences in categorical and continuous variables, respectively.

We are using difference-in-differences estimates because the change may inherently happen over time. Therefore, a control group will capture this intrinsic temporal change without DIPH intervention and subtract it from the change brought by the DIPH intervention to assess the net effect on key study outcomes i.e Health Information System performance and Governance of data-driven decision-making at the district level. First, we will calculate absolute differences in percentages from the baseline and the endline, then calculate the net-effect by subtracting the absolute DIPH- intervention difference from the control. We will use multilevel random regression to test the

intervention's impact (net-effect), accounting for observed and unobserved time-invariant and the time-variant factor between intervention and control sites.

We will include districts as level two variables with multilevel modelling to control intra-class correlation. The analysis will be adjusted for personal and professional characteristics of respondents and contextual factors of districts

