#### **Study Design**

A quasi-experimental study with pre and post comparisons will be applied. Study woredas will be considered as clusters and equal number will be allocated for presence and absence of intervention arm. The study will be conducted in all Woredas of North Shewa Zone by allocating 12 of them in intervention and 12 in non-intervention arms. A matched peer random allocation will be employed. To reduce subjective allocation, matching will be done based on Woredas' performance level and distance.

**Study area:** based on the criteria of a) receptiveness of the zonal health office, B) manageable distance from Addis Ababa, the Amhara region was shortlisted for the implementation phase of DIPH.

Amhara regional state consists of 10 administrative zones, one special zone, 105 Woredas, and 75 urban centres. Amharic is the working language of the state. The capital of the region is Bahir Dar, where Ethiopia's largest inland body of water, Lake Tana, is located. The state of Amhara covers an estimated area of 170,752 square kilometres, and its projected population for 2019 G.C. is 21,844,000.

The study will be implemented in North Shewa, one of the administrative zones in the Amhara region. Geographically, it is bordered in the south and west by the Oromia region, in the north by South Wollo, in the north-east by the Oromia Zone, and in the east by the Afar Region. The total area is 15,936.13 square km, with a population density of 115.30. According to the 2007 census conducted by the Central Statistical Agency of Ethiopia (CSA), this zone has a total population of 1,837,490. 11.66% are urban dwellers. Towns and cities in North Shewa include Ankober, Debre Berhan and Shewa Robit. Amharic is the first language of 92.97% of the population, followed by Oromiffa (6.32%). 94.71% of the population are Ethiopian Orthodox Christians. Details of selected maternal and child-health indicators and health-system infrastructure in the proposed administrative zone are given in Annex I, II and III.

This development phase has been successfully completed, and we anticipate the study will be implemented in all 24 Woredas of the North Shewa zone (i.e. 12 DIPH, 12 non-DIPH).

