**Implementation phase (August 2019-July 2021):** up to six four-monthly cycles of DIPH each will be conducted in the 12 woredas of North Shewa zone over 24 months (i.e. two fiscal years: the first year to complete the embedding of the strategy within the system, and the second year to establish effectiveness).

The Data-Informed Platform for Health will be implemented in the North Shewa administrative zone of the Amhara region. Its Woredas will be stratified by urban and rural, and 12 intervention and 12 comparison Woredas will be randomly selected in collaboration with the zonal health department.

**Embedding:** The Performance Review Team meetings of the district health administration, which is entrusted with integrating planning and facilitating data-driven and collaborative decision-making, will be used as a platform to introduce the DIPH. Activities will focus primarily on:

1. Strengthening the Performance Review Team forum for the engagement of all government and non-governmental stakeholders in order to identify challenges and solutions, and to assess resource allocation and responsibilities. These meetings will be convened with the aim of consensus-building and collective decision-making to improve health systems and services in their areas.
2. Promoting the critical review and regular use of local data to understand health-system progress at the Woreda level.

**Training:** Prior to the initiation of the first DIPH cycle, district health management staff of DIPH Woredas will be provided with three days' intensive residential training based on the specifically-designed curriculum (described above) in their zonal city. On average, six staff members per Woreda will be trained by the research team. Along with the Woreda's health department head, programme officers and an HMIS focal person, experts from the zonal health department will be included in the training. The three-day residential training will be conducted by the DIPH research investigators team

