1. Health Information System performance at the district level (the summary measure will be created based on the constructs of 1) essential infrastructure for data management, 2) data diversity, 3) reporting timelines, 4) data-quality assessment mechanisms, and 5) data use).
2. Governance of data-driven decision-making at the district level (the summary measure will be created based on the constructs of 1) evidence-based decision-making, 2) participatory decision-making, 3) understanding value of data, 4) health system support for data-use/data-driven decision-making, and 5) accountability).

The summary measures/indices will be calculated for each of the 24 Woredas at baseline and at endline, and will range from 0-100%. They will also be categorized to create indicators to determine proportion change for before and after comparison.

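### Woredas are allocated at random, yet the net effect subtracts the baseline instead of adjusting for it, which gives up precision by an amount the plan does not let the reader fix

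*Combined protocol and SAP*

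**What the plan says.** The Data Analysis Plan defines both primary outcomes as change relative to non-DIPH districts and gives one reason for its estimator: "We are using difference-in-differences estimates because the change may inherently happen over time". Baseline-to-endline differences are taken within each arm and subtracted between arms, and the resulting net effect is tested in a multilevel regression with district at level two. The adjustment variables are respondents' personal and professional characteristics and district context. The baseline value of the outcome is not listed.

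On allocation, Study Design says: "A matched peer random allocation will be employed", with matching on performance level and distance. Its implementation-phase paragraph describes urban/rural strata and says: "12 intervention and 12 comparison Woredas will be randomly selected". The first sentence of Study Design nevertheless labels the study quasi-experimental.

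On data, the evaluation-phase text says: "The summary measures/indices will be calculated for each of the 24 Woredas at baseline and at endline". A baseline index per woreda will therefore exist.

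**The concern.** If woredas are allocated at random, any baseline gap between arms is chance. The concurrent control arm then accounts for change over time in a plain endline comparison, so the stated reason does not call for subtracting the baseline.

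A change score sets the baseline coefficient to 1 whatever the true baseline-endline relation is. When that relation is weaker, the score over-corrects. Given a chance baseline gap d, the estimate is off by (1 - rho) x d in expectation; for example, an assumed gap of 5 points at rho 0.5 moves it by 2.5 points. Over repeated allocations this averages to zero, so it appears as extra variance and not as bias.

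The multilevel model does not cure this as described. With arm, time and arm-by-time terms it returns the same difference-in-differences. Only a baseline covariate, or a single baseline mean shared by both arms, recovers the precision, and neither is stated. All 24 woredas of the zone are already used, so power cannot be bought with more clusters there.

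**Working it through.** **Inputs from the sample-size formula under Table 1:** two-sided 5%, 80% power, proportions 0.50 and 0.75, k = 0.096942 in both arms, 6 staff per woreda (Table 1), 12 woredas per arm. The documents give no baseline-endline correlation and no measure of how well matching works, so both are varied as assumptions.

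**1. The plan's own figure.** Variance of one woreda mean:
- at 50%: 0.25/6 + 0.096942² x 0.25 = 0.04402
- at 75%: 0.1875/6 + 0.096942² x 0.5625 = 0.03654
- sum: 0.08055 (from unrounded values)

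c = 1 + 7.849 x 0.08055/0.0625 = 11.12, which rounds up to 12, as stated. (The legend's m = 72 would give 2.72, so only m = 6 reproduces it.) Power at 12 per arm: Φ(√(11 x 0.0625/0.08055) - 1.96) = 83%. The formula has no baseline variance term, so this is the power of an endline comparison.

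**2. General size, unmatched.** With equal variances at both waves, and in units of 2σ²/12:
- difference-in-differences: 2(1 - rho)
- baseline-adjusted: (1 - rho²) x 1.05, where 1.05 = 1 + 1/20 is the cost of estimating the slope from 24 woredas (normal baseline, 22 within-arm degrees of freedom)
- ratio: 2/[1.05(1 + rho)]

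| rho (assumed) | Formula | Simulation, 20,000 trials |
|---|---|---|
| 0.3 | 1.47 | 1.45 |
| 0.5 | 1.27 | 1.26 |
| 0.7 | 1.12 | 1.12 |
| 0.9 | 1.00 | 1.01 |
| 0.95 | 0.98 | 0.99 |

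Break-even is at 1 + rho = 2/1.05, so rho is about 0.90.

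**3. With matching.** Pairs were formed on a variable correlated r with the baseline index and randomised within pair; the adjusted model did not include the pairs. Simulated ratios (20,000 trials each):

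| rho | r = 0.5 | r = 0.7 | r = 0.9 |
|---|---|---|---|
| 0.3 | 1.37 | 1.26 | 1.12 |
| 0.5 | 1.21 | 1.15 | 1.07 |
| 0.7 | 1.09 | 1.07 | 1.03 |

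Matching makes a large d less likely, so there is less for the change score to over-correct.

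**4. The upper bound at the planning values.** Suppose staff answers are independent yes/no responses between waves. The woreda-level correlation can then be at most (0.096942 x 0.5)²/0.04402 = 0.053 in the control arm. In the DIPH arm it is at most 0.096942² x 0.5 x 0.75/√(0.04402 x 0.03654) = 0.088.
- Difference-in-differences variance, no correlation: 3 x 0.04402 + 0.03654 = 0.1686, which is 2.09 times 0.08055. Power: Φ(√(0.6875/0.1686) - 1.96) = 52%.
- Same, with woreda effects fully persistent: 3 x 0.25/6 + 0.1875/6 + (0.096942 x 0.25)² = 0.1568, ratio 1.95, power 55%.
- Baseline-adjusted: 83%, or about 81% after the slope cost (0.08055 x 1.05 = 0.08458).

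In this corner nearly all the gain comes from not subtracting the baseline; adjusting for it adds almost nothing.

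**The case against.** The strongest objection concerns the premise. The design is labelled quasi-experimental, woredas are selected in collaboration with the zonal health department, and the Health Bureau is also given a role in selecting them. Matching on performance and distance and stratifying by urban/rural are two different schemes. If the draw is not truly random, difference-in-differences is a defensible primary analysis and the preference for baseline adjustment no longer follows. This stands as a condition on the point. It does not remove it, because random allocation is stated twice and nothing says it was abandoned.

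Second, a reader might infer that the planned analysis has half the efficiency of the alternative and only about 52-55% power. The documents do not support that as a general statement. It needs six independent yes/no answers per woreda at each wave and no benefit from matching. The Data Analysis Plan defines a 0-100 summed index, much of the survey instrument records office-level facts such as equipment, guidelines and minutes, and all eligible staff are interviewed, so overlap between waves is possible. Rho could be well above 0.09.

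Third, a reader might infer that baseline adjustment is better at every correlation. With 24 woredas it is not: the two break even near rho 0.9, and difference-in-differences is about 1 to 2% better at 0.95.

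Fourth, this is not an error of validity. Difference-in-differences is unbiased under randomisation and fits outcomes worded as change. That is correct, and it limits the point to precision. Wording an outcome as change does not require a change score, since under randomisation both analyses estimate the same net effect.

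**Conclusion.** The point holds as one of precision. Given the stated random allocation, subtracting the baseline adds variance, and the reason offered for it is already met by the control arm. For unmatched allocation the variance ratio is about 1.5 at rho 0.3, 1.3 at 0.5, 1.1 at 0.7 and about 1 at 0.9 or above. Under effective matching on performance it is smaller, roughly 1.06 to 1.2 at rho 0.5. A ratio near 2 is a ceiling at the planning values and may not apply to the 0-100 index.

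The conclusion rests on the draw being random. The figures further rest on assumed correlations, roughly normal woreda indices and, in steps 2 and 3, equal variance at both waves. Adjustment can lose very little and may gain appreciably, so the change is worth making, but the planned analysis is not invalid without it.

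**What to change.** In the Data Analysis Plan, name as primary a regression of the endline woreda index on arm and baseline woreda index. The alternative is a multilevel model with one baseline mean common to both arms and no arm main effect at baseline. Include the matched pairs or strata actually used, and report the net effect with a confidence interval. Keep difference-in-differences as a sensitivity analysis. Settle this before endline data are analysed, so that the estimator is not chosen on results.

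In Study Design, reconcile the quasi-experimental label with the stated random allocation and say which scheme was used (matched pairs, urban/rural strata, or both), because the choice of primary analysis depends on it.

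The cost is wording only, since the baseline index is already planned for every woreda. The downsides are one degree of freedom for the baseline slope, more if pairs are modelled, and reliance on the random draw, which the sensitivity analysis helps to check.

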## Strengths and limitations of the DIPH project

The overall strength of this study is that it enables the intervention Woredas to use their locally generated data for decision making.

Since the effectiveness of the intervention will be conducted in 12 Woredas in one zone in Amhara region, if the intervention is effective, the study findings will be further scaled-up in a wider setting.

## Communication and dissemination of study findings

After the conduct of the study, study results will be disseminated through dissemination workshop by inviting the Federal Ministry of Health, North Shewa Zonal health office, Amhara Regional health bureau and other relevant stakeholders.

From the final study findings, manuscript will be prepared and submitted to relevant peer reviewed scientific journals for publication.

## Ethical considerations and review process

Timely ethical clearance will be sought at the Ethical Review Board of the Ethiopian Public Health Institute, and at the corresponding board at the London School of Hygiene and Tropical Medicine.

The study does not involve data-collection from community members or health records. The study participants are health-system officials, and the template of a consent form for their interviewees with a standard introduction to, and explanation of, the project is attached (Annex IV).

## Voluntary participation

Participation in this study is completely voluntary and the participants are free to withdraw at any time without giving any reason and without any negative consequences.

## Confidentiality

The researchers will not identify study participants by name in any reports and confidentiality as a participant in this study will remain secure. Subsequent use of data will be subject to standard data use policies that protect anonymity of study participants.

## Privacy

During data collection from study participants; privacy will be secured, no one will be around. Field staff are committed to collect personal information responsibly.

## Implementation of DIPH project

No	Activities	19	19	19	19/20	20	20	20/21	21	21	21
	Year	19	19	19	19/20	20	20	20/21	21	21	21
	Months	May	June	Jul-Oct	Nov-Feb	Mar-Jun	Jul-Oct	Nov-Feb	Mar-Jun	July	Aug-Nov
	Developmental phase										
1	Ethics/IRB submission										
2	Baseline survey										
	Implementation phase										
3	DIPH training										
4	DIPH cycles			C1	C2	C3	C4	C5	C6		
	Evaluation phase										
	DIPH cycle Monitoring										
5	End-line survey										
6	Data cleaning, Analysis & reporting										
7	Dissemination										

## Benefits of the Study's Results

The overall aim of the Data-Informed Platform for Health (DIPH) is to improve health programmes and services at the Woreda level. As an innovation to strengthen health systems, the DIPH promotes the sharing and use of local data for health-decision-making, particularly problem-solving. Key health-data on inputs and processes from multiple programmatic activities at the district-health administration level are brought together. This data then informs the collaborative action-plan and follow-up of different government departments and private sector agencies through a structured process that uses existing platforms at the district level. This resonates closely with the Ethiopian Health Sector Transformation Plan in 2015 [6], which identifies the information revolution as part of its transformation agenda. Promoting a culture of information-use at, or close to, the point of collection is central to the information revolution.

### Importance of DIPH in Health System Strengthening

1. **Inter-sectoral convergence**, through effective coordination with key departments to address health determinants, including water, sanitation, hygiene, nutrition; education; gender and women-empowerment; and integrated Child health and Development services etc.;
2. **Multi-sectoral data-sharing;**
3. **Strengthening data-quality**, aiming to rationalize regular use of local HMIS indicators; and reliable health-data/data-triangulation mechanisms; and
4. **Accountability and planning**, through regular meetings of Performance Review Team dedicated to periodic review progress and a re-calibrated future road map, such meetings having a clear agenda and follow-up action with regular, focused reviews at different levels.

